**Rx TREATMENT**

Randomization/drug assignment		✓																
Administration of injectable study drug/placebo; retain unused carton sealed or empty carton without syringe.		✓	✓	✓	✓	✓	✓	✓	✓	✓	✓	✓	✓	✓	✓			
Dispense study drug		✓	✓	✓	✓	✓	✓	✓	✓	✓	✓	✓	✓	✓	✓			
Perform blinded drug accountability and reconciliation, retain unused carton sealed or empty carton without syringe (instruction for retaining cartons is not relevant to Week 24, Un-scheduled Visit, or PD Visit).			✓	✓	✓	✓	✓	✓	✓	✓	✓	✓	✓	✓	✓	✓	✓	

## APPENDIX E. PROTOCOL SUMMARY OF CHANGES

Protocol	Date
Version 1.0	17 October 2018
Version 1.1 (VHP Countries: Czech Republic, Denmark, Finland, Germany, Hungary, Italy, Norway, Poland, Spain, Sweden, United Kingdom)	18 February 2019
Version 1.2 (Ireland only)	18 February 2019
Administrative Change 1	31 May 2019
Version 1.3 (United States only)	25 June 2019
Version 2.0	13 March 2020
Version 2.1 (Ireland only)	13 March 2020
Version 2.2 (VHP countries)	31 July 2020
Version 3.0	28 October 2020
Version 2.2.1 (VHP countries)	29 October 2020

### Summary of Protocol Changes:

- Section 4.1 Overall Study Design and Plan
  - Specified that a Week 24 database lock will be conducted to perform the Primary Analysis.  
**Rationale:** To clarify the timing of the Primary Analysis.
- Section 5.8 Randomization/Drug Assignment
  - Clarified that AbbVie personnel will remain blinded until the Week 24 database lock.  
**Rationale:** To be consistent with Section 4.1.
- Section 7.1 Statistical and Analytical Plans
  - Specified that the SAP will be finalized prior to the Week 24 database lock.  
**Rationale:** To be consistent with Section 4.1.

## APPENDIX F. OPERATIONS MANUAL

1.0 Introduction

This Statistical Analysis Plan (SAP) describes the statistical analyses for upadacitinib Study Protocol M16-046, A Multicenter, Randomized, Double-Blind, Double-Dummy, Active Controlled Study Comparing the Safety and Efficacy of Upadacitinib to Dupilumab in Adult Subjects with Moderate to Severe Atopic Dermatitis.

Study M16-046 examines the efficacy and safety of upadacitinib in subjects with moderate to severe atopic dermatitis.

The analyses of biomarker and pharmacokinetic endpoints will not be covered in this SAP.

The SAP will not be updated in case of administrative changes or amendments to the protocol unless the changes impact the analysis.

Unless noted otherwise, all analyses will be performed using SAS Version 9.4 (SAS Institute Inc., Cary, NC 27513) or later under the UNIX operating system.

This SAP includes changes to analyses described in the protocol. Details are outlined in Section 12.0.

2.0 Study Design and Objectives

2.1 Objectives and Hypotheses

The objective of this study is to evaluate the efficacy and safety of upadacitinib versus dupilumab for the treatment of adult subjects with moderate to severe atopic dermatitis (AD) who are candidates for systemic therapy.

2.2 Study Design Overview

This is a Phase 3b, randomized, double-blind, double-dummy, active comparator-controlled multicenter study that will evaluate the safety and efficacy of upadacitinib versus dupilumab in adults (≥ 18 to ≤ 75 years of age) with moderate to severe AD who

[figure not shown]
are candidates for systemic therapy. Eligible subjects must have a documented history of inadequate response to treatment with topical AD treatments or documented use of systemic treatment for AD within 6 months prior to the Baseline Visit or for whom topical treatments are otherwise medically inadvisable.

The study is comprised of a 35-day Screening Period, a 24-week double-blind treatment period, and an End-of-Treatment Follow-up Visit. The End-of-Treatment Follow-up Visit will be 12 weeks after the last injection. Subjects who meet eligibility criteria will be randomized in a 1:1 ratio to one of the two arms as shown below:

- Treatment A (N = 325): Daily oral doses of upadacitinib 30 mg from the Baseline visit until the Week 24 visit, and placebo pre-filled syringe administered at the baseline visit (2 subcutaneous [SC] injections), followed by placebo pre-filled syringe (1 injection) every other week until the Week 22 visit.
- Treatment B (N = 325): Dupilumab 600 mg (2 × 300 mg dupilumab SC injection) administered at the Baseline visit, followed by dupilumab 300 mg SC injection every other week until the Week 22 visit and daily oral doses of placebo tablets from the Baseline visit until the Week 24 visit.

Randomization will be stratified by baseline disease severity (moderate validated Investigator Global Assessment for atopic dermatitis [vIGA-AD 3] vs. severe [vIGA-AD 4]) and age (< 40, ≥ 40 to < 65, ≥ 65 years). The subject's age at baseline will be used for randomization and throughout the duration of the study.

The schematic of the study is shown in [Figure 1](#).

Figure 1. **Study Schematic**

BL = Baseline; SC = subcutaneous

* Dupilumab 300 mg SC injection will be administered every other week starting at the Week 2 visit and until the Week 22 visit, after an initial dose of 600 mg at the Baseline visit.

2.3 Treatment Assignment and Blinding

Subjects will be randomized to upadacitinib or dupilumab in a 1:1 ratio. Randomization will be stratified by baseline disease severity (moderate [vIGA-AD 3] vs. severe [vIGA-AD 4]), and age (< 40, \geq 40 - < 65, \geq 65).

The AbbVie study team, study site personnel, and subjects will be blinded to treatment assignment until the primary analysis. Thereafter, all study site personnel involved in the study and subjects will remain blinded to the subject's treatment throughout the study. The exception to this is the designated unblinded site staff responsible for administration of the injectable study drug who are unblinded for the entirety of the study.

2.4 Sample Size Determination

Approximately 650 subjects (18 - 75 years old) will be randomized to upadacitinib 30 mg or dupilumab in a ratio of 1:1 (325 subjects per treatment group). Assuming an EASI 75 response rate of at most 50% in the dupilumab arm, this sample size will provide more than 80% power to detect at least a 12% treatment difference using two-sided test at a 0.05 significant level. The assumption of dupilumab response rate for EASI 75 at Week 16 and 12% treatment difference were based on the pooled response rates of dupilumab Phase 3 monotherapy studies (SOLO 1 and SOLO 2) and the response rate of upadacitinib 30 mg in the upadacitinib AD Phase 2b study.

3.0 Endpoints

3.1 Primary Endpoint

The primary endpoint is:

- Proportion of subjects achieving a 75% reduction in EASI from Baseline (EASI 75) at Week 16.

3.2 Secondary Endpoints

Ranked Secondary Endpoints:

- Percent change in Worst Pruritus numerical rating scale (NRS) from Baseline at Week 16
- Proportion of subjects achieving a 100% reduction in EASI (EASI 100) at Week 16
- Proportion of subjects achieving a 90% reduction in EASI (EASI 90) at Week 16
- Percent change in Worst Pruritus NRS from Baseline to Week 4
- Proportion of subjects achieving a 75% reduction in EASI (EASI 75) from Baseline at Week 2
- Percent change in Worst Pruritus NRS from Baseline to Week 1

- Proportion of subjects achieving an improvement (reduction) in Worst Pruritus NRS ≥ 4 from Baseline at Week 16.

3.3 Other Efficacy Endpoints

All variables listed as primary or secondary endpoints will be analyzed at all visits other than Week 16. In addition, the following variables will be analyzed at all visits:

- Proportion of subjects achieving 75% reduction in EASI in the head and neck body region from Baseline
- Proportion of subjects achieving 75% reduction in EASI in each body region (other than head and neck) from Baseline

Proportion of Subjects Achieving an Improvement (Reduction) in Daily Worst Pruritus NRS ≥ 4 from Baseline for Subjects with Daily Worst Pruritus NRS ≥ 4 at Baseline by Day Up to Day 28

3.4 Safety Endpoints

The following safety evaluations will be performed during the study:

- Treatment-emergent AEs (TEAEs);
- Serious adverse events (SAEs);
- Adverse events of special interest (AESIs);
- Other Safety Topics of Interest.
- AEs leading to discontinuation of study drug;
- Vital signs and laboratory tests

4.0 Analysis Populations

The following populations will be used for the analyses.

The Intent-to-Treat (ITT) Population includes all randomized subjects. The ITT Population will be used for all efficacy analyses. Subjects will be included in the analysis according to the treatment groups that they are randomized to.

The Per-Protocol (PP) Population will include ITT subjects which excludes subjects with major protocol deviations that potentially affect the primary efficacy endpoint. The final criteria and the exclusion of subjects from the per-protocol population will be finalized before unblinding data for the Primary Analysis.

The Per-Protocol Population will exclude the subjects who violate any of the following criteria:

- Receive 80% of planned study drug, per randomization, before Week 16
- Have an EASI assessment post-baseline on or before Week 16
- Meet all the following disease activity criteria:
 - EASI score ≥ 16 at the Baseline Visits;
 - vIGA-AD score ≥ 3 at the Baseline Visits;
 - $\geq 10\%$ BSA of AD involvement at the Baseline Visits;
 - Baseline weekly average of daily worst pruritus NRS ≥ 4 . Note: The baseline weekly average of daily worst pruritus NRS will be calculated from the 7 consecutive days immediately preceding the Baseline Visit. A minimum of 4 daily scores out of the 7 days is needed.
- Must not have used the following AD treatments within the specified timeframe prior to Baseline Visit, per assessment of eligibility criterion 16 in the protocol:
 - Systemic therapy for AD, including but not limited to corticosteroids, methotrexate, cyclosporine, azathioprine, phosphodiesterase type 4 (PDE4)-inhibitors, interferon-gamma (IFN- γ) and mycophenolate mofetil within 4 weeks;
 - Targeted biologic treatments (refer to Section 5.3 of the protocol) within 5 half-lives [if known]) or within 12 weeks, whichever is longer;

- Phototherapy treatment, laser therapy, tanning booth, or extended sun exposure that could affect disease severity or interfere with disease assessments within 4 weeks;
- Oral or parenteral traditional Chinese medicine within 4 weeks;
- Marijuana use within 2 weeks;
- Topical treatments (with the exception of topical emollient treatments, described in Eligibility Criterion 8), including but not limited to TCS, TCIs, or topical PDE-4 inhibitors within 7 days.

Per-protocol Population will be fully defined in the classification plan and the exclusion of subjects from the Per-protocol Population will be finalized before blind break.

The Safety Population consists of all subjects who received at least 1 dose of study drug including matching placebo. For the safety population, subjects are assigned to a treatment group based on the "as treated" treatment group, regardless of the treatment randomized. The "as treated" is determined by the treatment the subject received during the majority of the subject's drug exposure time in the analysis period if any mis-dosing occurs.

5.0 Subject Disposition

The total number of subjects who were screened, enrolled (randomized), and reasons for exclusion, including screen failure, will be summarized.

The number of subjects for each of the following categories will be summarized for each treatment group in the ITT Population:

- Subjects enrolled (randomized) in the study;
- Subjects who took at least one dose of study drug;
- Subjects who took at least one dose of active study drug;
- Subjects who completed protocol-specified treatment;
- Subjects who prematurely discontinued study drug (all reasons and primary reason);

- Subjects who prematurely discontinued study (all reasons and primary reason);
- Subjects who completed the study
- Subjects who were rescued in the study
- Subjects who enrolled to M19-850

Number and percentage of subjects who discontinued study drug and who discontinued from study will be summarized by reason (primary reason and all reasons) for each treatment group and overall. Subjects with multiple reasons for premature discontinuation will be counted once in the calculation of the number and percentage of total discontinuations.

In addition, a disposition table of the below categories will be summarized:

- Subjects who took at least one dose of study drug before Week 16;
- Subjects who took at least one dose of active study drug before Week 16;
- Subjects who completed Week 16;
- Subjects who prematurely discontinued study drug (all reasons and primary reason) before Week 16;
- Subjects who prematurely discontinued study (all reasons and primary reason) before Week 16;
- Subjects who were rescued in the study before Week 16

6.0 Study Drug Duration and Compliance

Study Drug Duration (in Days):

Summary of study drug duration and study drug compliance will be provided for each treatment group for the Safety Population 1) from Baseline to Week 16 visit and 2) the entire treatment period, respectively. Study drug duration (days) will be summarized using the number of subjects, mean, standard deviation, minimum, median and maximum for each treatment group.

1. From Baseline to Week 16:

- Duration of upadacitinib is defined for each subject as
 - The minimum (last dose date of upadacitinib, Week 16 visit date -1) minus first dose date of upadacitinib +1 if the Week 16 visit date is non-missing, and
 - The minimum (last dose date of upadacitinib, nominal Week 16 visit date-1) minus first dose date of upadacitinib +1 if the Week 16 visit date is missing. Here nominal Week 16 visit date is defined as first dose date of upadacitinib + 112.
- Duration of dupilumab is defined for each subject as the last dose date of dupilumab before Week 16) minus first dose date of dupilumab +14. The last dose of dupilumab before Week 16 is defined as the last dose date of dupilumab within 105 days (the upper bound of Week 14 dupilumab administration window) of the first dose date of dupilumab.

2. The entire treatment period:

- Duration of upadacitinib is defined for each subject as last dose date of upadacitinib minus first dose date of upadacitinib +1,
- Duration of dupilumab is defined for each subject as last dose date of dupilumab minus first dose of dupilumab date +14.

Compliance:

Treatment compliance will be summarized by treatment group in the Safety Population for 1) from Baseline to Week 16 visit and 2) the entire treatment period, respectively.

1. From Baseline to Week 16:

- Upadacitinib compliance is defined as the number of upadacitinib (or placebo for upadacitinib) actually taken prior to Week 16 (i.e., the difference between the number of tablets dispensed and the number of tablets returned) by the subject divided by the number of tablets planned to be taken by the subject during the first 16 weeks.

- Dupilumab compliance is defined as the number of dupilumab (or placebo for dupilumab) injections administered during the subject's participation prior to Week 16 by the subject divided by the number of injections planned during the subject's participation during the first 16 weeks.

2. The entire treatment period:

- Upadacitinib compliance is defined as the number of upadacitinib (or placebo for upadacitinib) actually taken (i.e., the difference between the number of tablets dispensed and the number of tablets returned) by the subject divided by the number of tablets planned to be taken by the subject during the study.
- Dupilumab compliance is defined as the number of dupilumab (or placebo for dupilumab) injections administered during the subject's participation up to Week 22 by the subject divided by the number of injections planned during the subject's participation during the study.

7.0 Demographics, Baseline Characteristics, Medical History, and Prior/Concomitant Medications

Demographics, baseline or disease characteristics, and medical history will be summarized for ITT overall and by treatment group. Categorical variables will be summarized with the number and percentage of subjects; percentages will be calculated based on the number of non-missing observations. Continuous variables will be summarized with descriptive statistics (number of non-missing observations, mean and standard deviation, median, minimum and maximum). Prior and concomitant medications will be summarized for the Safety Population overall and by treatment group.

7.1 Demographics and Baseline Characteristics

Subject Demographics

The following demographic and Baseline parameters will be summarized.

Subject Demographics

- Sex (Male, Female)
- Age (Years)
- Age Group (< 40 years, \geq 40 – < 65 years, \geq 65 years)
- Race (White, Black, American Indian/Alaska Native, Native Hawaiian or Other Pacific Islander, Asian, Other)
- Ethnicity (Hispanic or Latino, not Hispanic or Latino)
- Body weight (kg)
- Height (cm)
- BMI (kg/m^2)
- BMI (normal: < 25, overweight: \geq 25 – < 30, obese: \geq 30)
- Geographic Region (US/Puerto Rico/Canada and Other)
- Tobacco/Nicotine and Alcohol Use
 - Tobacco/Nicotine Use (unknown, never, current, former)
 - Alcohol Use (unknown, never, current, former)

Baseline Characteristics

- Baseline vIGA-AD (< 4, 4)
- Baseline EASI (< median, \geq median)
- HS CRP (< median, \geq median)
- Immunoglobulin E (IgE)
- Previous systemic therapy (with and without)
- EASI overall score and body region scores
- Body Surface Area (BSA) in percentage
- Worst Pruritus NRS (Weekly Average)
- Worst Pruritus NRS (Daily Score)
- Head and Neck Patient Global Impression of Severity (HN-PGIS)
- Atopic Dermatitis Impact Scale (ADerm-IS)

- Disease duration since diagnosis (years)
- Disease duration since symptoms started (years)
- Duration between symptoms and diagnosis (years)
- Prior Atopic Dermatitis Treatment
- TB Status: Tuberculin PPD skin test result, QuantiFERON-TB Gold test result, Latent TB(Yes/No)
- Chest x-ray
 - Normal, Abnormal
 - Calcified granulomas (Absent, Present)
 - Pleural scarring (Absent, Present)
 - Pleural thickening (Absent, Present)
 - Indicative of previous TB infection (Yes, No)

7.2 Medical History

Medical history data will be coded using the Medical Dictionary for Regulatory Activities (MedDRA). The actual version of the MedDRA coding dictionary will be noted in the statistical tables and clinical study report. The number and percentage of subjects in each medical history category (by MedDRA system organ class and preferred term) will be summarized overall and by treatment group. The system organ class (SOC) will be presented in alphabetical order, and the preferred terms will be presented in alphabetical order within each SOC. Subjects reporting more than one condition/diagnosis will be counted only once in each row (SOC or preferred term).

Medical history will be summarized in the ITT Population.

7.3 Prior and Concomitant Medications

Prior and concomitant medications will be summarized by generic name. A prior medication is defined as any medication taken prior to the date of the first dose of study drug. A concomitant medication is defined as any medication that started prior to the date of the first dose of study drug and continued to be taken after the first dose of study drug

or any medications, other than study drug, taken after the first dose of study drug and within 1 day of the last dose of study drug for the subjects on upadacitinib, and within 14 days of the last dose of study drug for the subjects on dupilumab, respectively.

Medications taken on the day of the first dose of study drug are counted as concomitant medications. The number and percentage of subjects taking medications will be summarized by generic drug name based on the World Health Organization (WHO) Drug Dictionary for both prior and concomitant medications.

Prior and concomitant medications will be summarized in the Safety Population.

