8.2.1 Categorical Endpoints

- The primary approach for handling missing data in the analysis of categorical endpoints (including the primary endpoint) will use Non-Responder Imputation while incorporating Multiple Imputation (MI) to handle missing data due to COVID-19 (NRI-C).

The NRI-C will categorize any subject who does not have an evaluation during a pre-specified visit window (either due to missing assessment or due to early withdrawal from the study) as a non-responder for the visit. The only exceptions are: 1) when the subject is a responder both before and after the visit window, the subject will be categorized as a responder for the visit. 2) missing data due to COVID-19 infection or logistical restriction will be handled by Multiple Imputation. In addition, all assessments after the start of rescue medications will not be included in the analyses; as a result, subjects will be counted as non-responders thereafter and will not be imputed by MI. NRI-C will not be applied to the endpoint of improvement of daily Worst Pruritus NRS ≥ 4 up to Day 28.

- A sensitivity analysis for categorical endpoints will use NRI with No special data handling for missing due to COVID-19 (NRI-NC).

NRI-NC will be performed in the same way as NRI-C without the exception #2 above. That is, missing due to COVID-19 infection or logistical restriction will also be counted as non-responders.

Subjects whose change/percent change from Baseline cannot be calculated because of a missing Baseline will be considered as a non-responder at all post-baseline visits in both NRI-C and NRI-NC approaches. NRI-NC will be primary approach for the efficacy endpoint of improvement of daily Worst Pruritus NRS ≥ 4 up to Day 28.

- Multiple Imputation (MI), a sensitivity analysis for the primary endpoint and key secondary categorical endpoints: Markov Chain Monte Carlo (MCMC) will be first applied to augment data into monotonic missing pattern and PROC MI will be used to generate 30 datasets using the regression method. The variables to be included in the imputation model are: treatment group, stratum (vIGA-AD categories), gender, Baseline, and measurements at each visit up to the end of the analysis period. The random seed for MCMC and the random

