seed for PROC MI are specified in [Appendix E](#). The imputed post-baseline measurements will be rounded to the same precision as the observed data before the determination of responder status. Subjects will be characterized as responders or non-responders based on MI imputed datasets. Using the CMH model adjusted by the stratification factor (vIGA-AD categories), the imputed endpoints will be analyzed using each of the 30 datasets. SAS PROC MIANALYZE will be used to generate the final inferences of the risk difference between upadacitinib group and dupilumab group. Note that measurements will be considered as missing after the first dose of rescue treatment before MI. Regardless of MI imputed values, subjects after receiving rescue medications will be counted as non-responders.

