Appendix G. Rescue Definition

The topical and systemic medications for AD therapy are coded to the following drug classes. Among these AD medications, the potential AD rescue medications are determined through a medical review process.

3. Plain Topical Corticosteroids
4. High Potency Topical Corticosteroids
5. Medium Potency Topical Corticosteroids
6. Low Potency Topical Corticosteroids
7. Topical Calcineurin Inhibitor Therapy
8. Other Topical therapy (not including moisturizers/emollients)
9. Biologic Systemic Therapy
10. Non-biologic systemic therapy
11. Other Systemic Therapy
12. Phototherapy

Concomitant medications (with the start date after the first date of study drug) that are categorized as "potential AD rescue" per medical review AND in categories 1 – 10 above are considered as rescue medications.

The medical review process is documented in the Rescue Medication Medical Review Process – Upadacitinib AD.

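### Do the arm-specific concomitant-medication windows in SAP 7.3 carry over into the rescue definition that sets non-response?

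*SAP*

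**What the plan says.** SAP 7.3 defines a concomitant medication for descriptive tables. A medication taken after the first dose qualifies only up to a limit that differs by arm: "within 1 day of the last dose of study drug for the subjects on upadacitinib, and within 14 days of the last dose" for dupilumab. The section then states its use: "Prior and concomitant medications will be summarized in the Safety Population".

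SAP Appendix G defines rescue. It starts from "Concomitant medications (with the start date after the first date of study drug) that are categorized as" potential rescue by medical review and fall in the listed drug classes, which include systemic therapy and phototherapy. It gives a start condition and no end condition, and it does not cite 7.3. It adds: "The medical review process is documented in the Rescue Medication Medical Review Process". That document is not among those supplied.

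The rescue flag matters. Under NRI-C in SAP 8.2.1, "all assessments after the start of rescue medications will not be included in the analyses", and the subject is a non-responder from then on. NRI-NC follows the same rule. In the MI sensitivity analysis, "subjects after receiving rescue medications will be counted as non-responders" whatever value is imputed. SAP 8.2.2 drops post-rescue measurements from the MMRM.

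Protocol 5.4 has study drug stopped for good before systemic rescue or phototherapy begins, and encourages those subjects to keep attending visits.

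**The concern.** Appendix G uses a term that the SAP defines once, and that definition treats the arms differently. Read literally, the same therapy started on, say, day 7 after the last dose counts as rescue on dupilumab and not on upadacitinib. The event that sets non-response in the primary analysis would then depend on treatment arm.

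Protocol 5.4 makes the situation foreseeable, since both off-drug therapy and off-drug Week 16 EASI assessments are expected. The sensitivity analyses would not expose the problem, because NRI-NC and MI use the same flag. The per-protocol analysis uses NRI-C (SAP 8.3.4), and its 80% drug criterion needs about 0.8 × 112 = 89.6, so 90 tablets. It can therefore keep a subject who stops after about day 90. At stake would be a comparison tilted towards the sponsor's drug in a superiority trial.

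**Working it through.** **1. The plan's own figure.** SAP 2.4 claims more than 80% power for 50% versus 62%, 325 per arm, two-sided 0.05. With pooled null variance:

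z = [0.12 × √325 − 1.96 × √(2 × 0.56 × 0.44)] / √(0.50 × 0.50 + 0.62 × 0.38) = (2.163 − 1.376) / 0.697 = 1.13, so power is 87.1%.

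The claim holds, and the rescue question does not alter it.

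**2. Which reading fits the text?**

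| Place | What it implies |
|---|---|
| SAP 7.3 | Limits serve generic-name summaries in the Safety Population; rescue and efficacy are not mentioned |
| SAP Appendix G | Own date condition (start after first study drug), which differs from 7.3, where therapy begun before first dose and continued also counts |
| SAP 8.2.1, 8.2.2, Appendix F 2.1 and 2.4 | Rescue acts from its start onward, with no limit tied to last dose |
| SAP 5.0 | Counts "Subjects who were rescued in the study before Week 16"; the limit is a study visit, the same in both arms |
| Protocol 5.4, Prior and Concomitant Therapy | Records any medication received during the study |
| Protocol 5.4, Rescue Therapy | Systemic rescue and phototherapy follow the end of study drug, so a 1-day limit would nearly empty those classes on upadacitinib |

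Only the shared term supports the asymmetric reading. The listed classes and the efficacy rules make sense only without an end limit.

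**3. Width of the gap if 7.3 did apply.** Counted from the last tablet, start days 2 to 14 give 13 days. SAP 6.0 suggests that the 14 days run from the last injection: "Duration of dupilumab is defined for each subject as last dose date of dupilumab minus first dose of dupilumab date +14". If the last tablet falls d = 0 to 13 days after the last injection, the gap is 14 − d − 1 = 13 to 0 days, mean 6.5.

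**4. Size, by assumption only.** Take no true difference (50% versus 50%, 325 per arm) and k upadacitinib responders wrongly kept.

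SE = √(2 × 0.25 / 325) = 0.0392; one-sided risk = Φ((k/325)/SE − 1.96).

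| k | Shift (points) | Risk |
|---|---|---|
| 0 | 0 | 2.5% |
| 1 | 0.3 | 3.0% |
| 2 | 0.6 | 3.6% |
| 3 | 0.9 | 4.2% |

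If 25–50% of subjects in the gap respond, k = 1 to 3 needs between 1/0.50 = 2 and 3/0.25 = 12 upadacitinib subjects in it, or 0.6% to 3.7% of 325.

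A wider assumed range, with 1–5% of upadacitinib subjects in the gap and 25–75% of them responding, gives shifts from 0.01 × 0.25 = 0.25 to 0.05 × 0.75 = 3.75 points, and two-sided rejection rates of 5.05% to 16.0%. The top end needs 0.05 × 325, about 16 upadacitinib subjects, to start therapy inside this short gap.

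**5. Direction.** Step 4 counts only the gap. Compared with an open-ended rule, the literal reading misses upadacitinib rescue from day 2 and dupilumab rescue from day 15. Let g be upadacitinib responders in the gap, and u and v the later-starting responders on upadacitinib and dupilumab. The net shift towards upadacitinib is (g + u − v)/325. It equals g/325 only if u = v, and it reverses if v > g + u. The documents give none of the three.

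**The case for a change.** The best case for a change is that a primary analysis should not depend on inference. The term is defined, the definition differs by arm, and two sentences would close the matter. Protocol 5.6 and 5.10 add some support: once study drug stops, the rescue and efficacy-driven discontinuation criteria cease to apply, and 5.10 says subjects then receive standard of care. A programmer might conclude that off-drug therapy is not rescue at all. In a double-dummy trial, 7.3 also leaves open whether the last dose is the last tablet or the last injection.

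Part of this stands. The SAP does not say in so many words that the 7.3 limits stop at the medication tables, and a cross-reference would be tidy. The protocol sentences, however, concern conduct after discontinuation; they do not define an analysis flag. Treating all off-drug therapy as not rescue would also be the same rule in both arms. The asymmetry arises only by importing the 7.3 limits into a section that does not cite them. The choice of last-dose date has no bearing on a rule without an end limit.

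**Conclusion.** No change follows. This is a gap in wording that analysts would fill sensibly: 7.3 governs summary tables, and rescue for efficacy runs from its start date in both arms. The separate medical-review document may already say so, but that cannot be checked here.

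If the 7.3 limits were applied, the affected subjects would be few. Each would have to stop drug before Week 16 without on-drug rescue, start therapy within a gap of at most 13 days, still be assessed at Week 16, and be an EASI 75 responder. Topical therapy comes first under protocol 5.4 and study drug may continue during it; such on-drug rescue counts in both arms on either reading. The 3.0–4.2% figures assume one to three such upadacitinib subjects and balanced later rescue. The documents supply neither number, so neither the size nor the direction of any net effect can be established.
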